*2. What is/are the research question(s)/specific aim(s)? Pose very specific questions that can be addressed within the proposed design of the study. Prioritize them in order of importance.*

The specific aim of the study is to determine whether the use of perioperative IV TXA, given prior to incision (concurrent with preoperative antibiotics) and then at wound closure, reduces the calculated total blood loss postoperatively in patients undergoing PAO when compared to a patients receiving placebo (normal saline). A 250 mL difference in blood loss will be considered a clinically important difference [18].

Secondary objectives of the study are to study whether the use of IV TXA reduces intraoperative cell saver utilization, transfusion of allogeneic blood, and hospital length-of-stay (LOS) compared to placebo use. We will also compare complications between study groups, including the incidence of clinically apparent deep vein thrombosis (DVT) and pulmonary embolism (PE), from postoperative day zero through 6 weeks postoperatively.

3. *What is/are the hypothesis(es)?*

**Hypothesis 1:** The use of IV TXA given prior to incision and at the time of wound closure will decrease the postoperative calculated total blood loss in patients undergoing PAO compared to patients receiving placebo.

**Hypothesis 2:** Patients receiving perioperative IV TXA will have lower intraoperative cell saver utilization, lower rate of allogeneic blood transfusion, shorter hospital LOS after PAO compared to patients receiving.

**Hypothesis 3:** There will be no difference in the rate of symptomatic venous thromboembolic events (VTE) (i.e., DVT and PE) in the 6 weeks after PAO surgery in patients who receive perioperative IV TXA compared to patients receiving placebo.

4. *Identify and define the primary outcome and when the outcome will be measured. If measuring change in post-operative function is the most important, that will be your primary outcome.*

Postoperative calculated total blood loss after PAO, determined from estimated blood volume [19], change in postoperative hemoglobin (preoperative hemoglobin – final inpatient hemoglobin), and transfused hemoglobin [20,21].

5. *Identify and define the secondary outcome(s) and when they will be measured (list additional goals one at a time with their corresponding outcomes).*

Secondary outcomes:

1. Intraoperative cell saver utilization: cumulative mL of reinfusion, measured at the end of the case intraoperatively

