2. Postoperative allogeneic transfusion (units of packed red blood cells per patient)
3. Length of hospital stay (postoperative day of discharge after surgery)
4. Incidence of complications at 6 weeks postoperatively, specifically:
  - VTE (symptomatic of DVT or PE)
  - Infection (superficial, deep)
  - Hematoma
  - Seroma
  - Reoperation

Patients will not be followed longer than 6 weeks during this trial, as we are aware of no evidence to suggest that TXA will influence outcomes outside of the perioperative period.

The authors will create a data safety monitoring board (DSMB) that will meet once a quarter to capture any complications, including but not limited to: death, DVT, PE, and wound complications.

This will include anesthesia, surgical, nursing, and research representatives. The time frame for reporting adverse events will be 1 week. If any mortality is seen, or any increase in DVT or PE rates from the established incidence in the literature (i.e., 0.94% for symptomatic VTE), the study will be stopped. The senior author and principal investigator will contact the IRB directly if any of the above occurs. In accordance with the Hospital guidelines for TXA use, DVT, PE, stroke, transient ischemic attack (TIA) and myocardial infarction (MI) will be reported to the Department of Quality Management ([name]).

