*2. What is the background of the topic that you believe is important for the reviewer to know in considering this protocol, including prior studies by this research team. Describe strengths and deficiencies of prior studies; explain how this study fits in. Include references.*

No Level I evidence exists regarding the use of IV TXA during PAO. To our knowledge there is only one prior study (published as an abstract) of IV TXA in the PAO patient population [11]. The authors retrospectively analyzed two longitudinal cohorts before and after implementation of an IV TXA protocol. All 100 patients received PAO performed by a single surgeon. Total blood loss was

706.16mL versus 1020.6 mL (p=0.001), for the TXA group compared to the non-TXA group, respectively. The study also showed a decrease in transfusion rate from 58% to 24% with the use of tranexamic acid, with the mean number of units transfused decreasing from 1.02 to 0.28 (p=0.013). This study did not find an increased incidence of VTE associated with the use of tranexamic acid [11]. The primary weakness of this study is its design. It was retrospective comparative study, with unmatched cohorts. Thus, it provides Level III evidence.

3. *Identify specific gaps in current knowledge that this study is intended to fill.*

Multiple well-done studies and meta-analyses have shown that intravenous (IV) of TXA reduces postoperative bleeding and the need for transfusion after major orthopedic surgery, without demonstrably increasing the risk for postoperative complications, including venous thromboembolic events (VTE) [5-10]. However, there are no high-level studies of IV TXA during PAO. We intend to provide the Level I evidence in support of the use of IV TXA for this indication.

4. *How will answering these questions change clinical practice, change concepts about the topic or confirm the work of other investigators?*

We hypothesize that our results will confirm the work of Wingerter, et al [11]. If the use of IV TXA in the PAO patient population significantly reduces total blood loss, then it would provide an efficacious and inexpensive method for reducing postoperative morbidity after PAO.

5. *Is this a pilot study that could lead to a more definitive protocol or different study?*

No.

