The randomization schedule will be generated by the HSS Epidemiology & Biostatistics Core with the randomization list provided to the investigators prior to initiation of patient recruitment. It will be a double-blind experiment with all parties, except the pharmacy, being blinded to the randomization schedule (surgeon, anesthesiologist, research assistant, and patient). Patient recruitment will continue until a total of 80 patients are enrolled.

*Treatment Arms:*

PAO will be performed as per the study surgeon's routine practice. In general, the operative extremity and hemipelvis will be prepped and draped in the usual sterile fashion. Prior to incision, the anesthesiologist, who will be blinded to the study group, will administer either 10 mg/kg, up to a maximum of 1 g, of IV TXA (diluted in 50 mL of normal saline, with a maximum concentration of 100 mg/mL) or 50 mL of normal saline prepared by the pharmacy. Only anesthesiologists agreeing to participate in the study will be paired with the study surgeons. A Smith-Petersen approach will be used, and standard surgical techniques for intraoperative hemostasis will be utilized.

Intraoperatively, a cell saver will be used, and the volume (mL) of autotransfusion will be recorded. The ischial, pubic, supra-acetabular, and retro-acetabular osteotomies will be performed, and the surgeon will then re-orient the acetabular fragment to achieve the desired correction. Cortical screws will then be placed for definitive fixation. After all hardware is placed, the wound will be thoroughly irrigated and suctioned. The anesthesiologist will administer either a second dose IV TXA as described above or a 50 mL bolus of normal saline, as prepared by the pharmacy, and the wound will be closed in layers. Routine, daily inpatient CBC data will be reviewed. Inpatient and office records will be accessed to help identify postoperative complications.

*Outcome Measures*

Primary outcome: Calculated total blood loss.

Secondary outcomes of interest: Postoperative allogeneic blood transfusion, and intraoperative cell saver utilization.

Calculated total blood loss will be determined from the difference between the preoperative hemoglobin and the lowest postoperative hemoglobin during the hospital stay (or the lowest postoperative hemoglobin prior to transfusion). Based on hemoglobin balance, the estimated blood loss will be calculated according to the formula by Nadler et al. [19]:

Hospital for Special Surgery

IRB# \_\_\_\_\_

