Form 1 -Clinical Research Proposal Form

$$\text{Estimated Blood Volume (EBV)} = (k_1 \times \text{Height}^3 \text{ (m)}) + (k_2 \times \text{Weight (kg)}) + k_3$$

For men,  $k_1 = 0.3669$ ,  $k_2 = 0.03219$ , and  $k_3 = 0.6041$

For women,  $k_1 = 0.3561$ ,  $k_2 = 0.03308$ , and  $k_3 = 0.1833$

Multiplying the EBV by the hematocrit (Hct) gives the red blood cell (RBC) volume. As such, a change in the RBC volume can be calculated from a change in the Hct level [20, 21]:

$$\text{Total RBC volume loss} = \text{EBV} \times (\text{Hct Preop} - \text{Hct Postop})$$

Transfusions (mean volume per unit, mL) can be taken into account by calculating the total blood loss:

$$\text{Total blood loss (L)} = \text{Total RBC volume loss} + (\text{No. of Units Transfused} \times 0.285) / (\text{Hct Preop} - \text{Hct Postop}) / 2$$

The rate of perioperative blood transfusions, both intraoperative and postoperative, will be documented for analysis.

The criteria for transfusion of blood products will be a hemoglobin level of  $< 8.0$  g/dL or a hemoglobin level of  $< 10.0$  g/dL with clinical signs of symptomatic anemia (e.g., chest pain that was deemed to be cardiac in origin, congestive heart failure, unexplained tachycardia, or hypotension unresponsive to fluid replacement). Blood will be administered 1 unit at a time, and the presence of symptoms or signs will be reassessed. Of note, the chart of the patient will clearly indicate him/her as a study patient.

VTE prophylaxis will be standardized, with each patient receiving 3 weeks of prophylaxis with 325 mg of oral aspirin twice daily. All patients will also receive a comprehensive, multidisciplinary approach to postoperative care with mechanical (sequential compressive device) prophylaxis in-house, early mobilization with physical therapy, medical optimization, and regional anesthesia, if appropriate.

**4. What is the long-term significance? - state the potential long-term benefits of the study, why it is important and its potential significance.**

The risk of excessive blood loss and blood transfusion in young, healthy patients after elective surgery is an event that can be reduced with blood conservation protocols, which can include pharmacological agents like TXA. If the use of IV TXA in the PAO patient population significantly reduces total perioperative blood loss, then it would provide an efficacious and inexpensive method for reducing postoperative morbidity after PAO.

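### The blood-loss formula uses a constant labelled as volume per transfused unit as if it were red-cell volume; if the label is right, each unit counts for too much in the primary outcome

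*Combined protocol and SAP*

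**What the plan says.** Section C.3(g), Outcome Measures, builds calculated total blood loss in steps, and section D, Data Analysis, repeats them. Estimated blood volume (EBV) comes from height, weight and sex. Then "Multiplying the EBV by the hematocrit (Hct) gives the red blood cell (RBC) volume", and "a change in the RBC volume can be calculated from a change in the Hct level", so the patient's own loss is a red-cell volume: EBV × (preoperative Hct − postoperative Hct).

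The transfusion step follows: "Transfusions (mean volume per unit, mL) can be taken into account by calculating the total blood loss". The printed line, with its result in litres, is

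total = red-cell volume loss + (units × 0.285) / (Hct pre − Hct post) / 2.

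Neither section gives a hematocrit or red-cell fraction for a transfused unit, or says whether 0.285 is product volume or red-cell content.

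Two other places bear on this. Section A.4 defines the primary outcome from estimated blood volume, the change from preoperative to "final inpatient hemoglobin), and transfused hemoglobin". Section A.5 counts transfusion as "Postoperative allogeneic transfusion (units of packed red blood cells per patient"; the data lists in section C.3(b) likewise record units.

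**The concern.** Patient blood is multiplied by hematocrit before it enters the balance, and transfused blood is not. A unit of packed cells is not all red cells, so a product volume used in place of a red-cell volume credits the patient with losing more than was replaced. The label points to product volume, whereas section A.4 calls for a content. The label also gives mL for a number that only makes sense in litres.

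The quantity affected is the primary outcome, and it also drives the interim efficacy test in section D. The excess grows with the number of units, and Hypothesis 2 in section A.3 expects less allogeneic transfusion under TXA. If that happens, part of the measured blood-loss benefit would be an artefact of how units are counted.

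**Working it through.** **1. The plan's own figure.** Sections C.2(c) and D give a 250 mL difference, SD 383.27 mL, two-sided alpha 0.05 and 40 per arm for 82% power. The standardised difference is 250 / 383.27 = 0.652. A two-sample t-test then has 82.1% power at 40 per arm, and 82% power needs 39.85 per arm. The sample size reproduces, and this point does not change it.

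**2. Inputs.** From the documents:
- 0.285 L per unit (C.3(g), D).
- The cited retrospective cohort, with "the mean number of units transfused decreasing from 1.02 to 0.28" (B.2): a difference of 1.02 − 0.28 = 0.74 units.
- The site's 33.3% transfusion rate (A.1) and the cohort's 58.6% relative reduction (B.1).

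Assumed, because the documents give no figure:
- Unit hematocrit 0.55 to 0.80.
- Mean patient hematocrit 0.335 to 0.35, used as the divisor that turns red cells into whole blood. This divisor is not the printed one (step 5).
- One unit per transfused patient in the site scenario, so the difference is 0.333 × 0.586 = 0.195 units.

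**3. Excess per unit.** If 0.285 L is product volume with hematocrit h, its red-cell content is 0.285 × h. With divisor m, the excess is 0.285 × (1 − h) / m.

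| h | Red cells per unit (L) | Excess, m = 0.335 (mL) | Excess, m = 0.35 (mL) |
|---|---|---|---|
| 0.55 | 0.157 | 383 | 366 |
| 0.60 | 0.171 | 340 | 326 |
| 0.70 | 0.200 | 255 | 244 |
| 0.80 | 0.228 | 170 | 163 |
| 1.00 (0.285 L is already red cells) | 0.285 | 0 | 0 |

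**4. Difference between arms.** Multiply the excess by the difference in mean units, taking a common divisor in both arms.
- Site scenario, 0.195 units, h from 0.55 to 0.80: 75 to 33 mL at m = 0.335; 71 to 32 mL at m = 0.35.
- Cited cohort, 0.74 units, same range of h: 283 to 126 mL at m = 0.335; 271 to 121 mL at m = 0.35.
- Equal units: 0 mL.

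**5. The line as printed.** Only the transfusion term is divided, and the divisor comes from the hematocrit drop, not the mean. Take an illustrative woman (assumed 1.65 m, 65 kg, Hct 0.40 falling to 0.27):
- EBV = 0.3561 × 1.65³ + 0.03308 × 65 + 0.1833 = 3.93 L.
- Red-cell loss = 3.93 × 0.13 = 0.511 L.
- No units: the printed line gives 0.51 L. Dividing by the mean hematocrit gives 0.511 / 0.335 = 1.53 L.
- One unit, as printed: 0.511 + 0.285 / 0.13 / 2 = 1.61 L.
- One unit, both terms divided by the mean hematocrit, h = 0.60: (0.511 + 0.171) / 0.335 = 2.04 L.
- The same with the unit counted as all red cells: (0.511 + 0.285) / 0.335 = 2.38 L, which is 340 mL more.

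The printed total for this transfused patient is therefore below the converted one, because her own red-cell loss is never turned into whole blood. The constant still matters on the printed line: at a drop of 0.13 its excess is 0.285 × (1 − h) / (2 × 0.13), or 493 mL at h = 0.55 and 219 mL at h = 0.80.

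**The case against.** The strongest reply is that nothing shows 0.285 L to be product volume. The label is loose and already carries the wrong unit, section A.4 speaks of hemoglobin content, and the formula rests on cited sources that the documents do not reproduce. If 0.285 L is red-cell content with a poor label, the excess is nil. This stands, and the size must be read as conditional. It does not remove the need to act, because the label and the use disagree and someone computing the outcome from the text cannot tell which to follow.

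A reader might infer that every transfused unit overstates a patient's total blood loss, and that the TXA effect is therefore exaggerated. The documents do not support either step. On the printed line the illustrative total is too low (1.61 L against 2.04 L). A between-arm bias needs a difference in units: the constant amplifies a real difference in transfusion and does not create an effect where TXA does nothing.

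A reader might also infer that the historical mean and SD are inflated. That is speculation. With 0.285 / 0.35 = 814 mL per unit and 33.3% of patients given one unit, the transfusion term alone would have SD 814 × √(0.333 × 0.667) = 384 mL. That equals the whole reported SD of 383.27 mL and leaves no room for other variation unless the terms covary negatively. This casts doubt on whether the assumed formula produced those data, so the question for the sponsor is how they were computed.

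Finally, the 120 to 280 mL range relies on a cohort in which 58% of the non-TXA group were transfused. This site's rate is 33.3%, so the 30 to 75 mL range is closer to the planned population, and even that borrows the cohort's relative reduction.

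**Conclusion.** The point holds in conditional form. As labelled, the rule uses a product volume where a red-cell volume is needed, and it conflicts with section A.4. Each unit's contribution is then too large by about 160 to 380 mL. If TXA reduces units, the apparent effect gains about 30 to 75 mL in the site scenario, or about 120 to 280 mL with the cited cohort's counts. Against the 250 mL target, the low end is about 13% (32 / 250) and the high end exceeds it. All of this rests on the assumed unit hematocrits and on a mean-hematocrit divisor that the plan does not print. The excess is zero if 0.285 L is already red-cell content, and with equal units the mean difference is unbiased.

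The constant is not the only fault in the line, nor the larger one: correcting it alone would not give a valid total blood loss.

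**What to change.** In sections C.3(g) and D, replace units × 0.285 with units × red-cell volume per unit, and define that volume. If 0.285 L is product volume, use 0.285 L × a unit hematocrit fixed in advance from the blood bank's product figure. If it is already red-cell content, relabel it and give the source. Correct mL to L, and make the wording agree with section A.4.

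Repair the divisor and brackets in the same edit, so that both terms are converted:

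total blood loss (L) = [EBV × (Hct pre − Hct post) + units × red-cell volume per unit] / [(Hct pre + Hct post) / 2].

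Check whether the historical 1296 ± 383 mL used the same constant. If it did, recompute it and confirm the sample size.

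The cost is one line of the analysis plan, one figure from the blood bank and possibly a re-run of the historical calculation. The number of units is already recorded. The downside is that the estimated TXA effect may be less favourable.

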**A. SPECIFIC AIMS OR RESEARCH QUESTIONS - answer each question individually.**

*1. What is the condition or intervention to be studied?*

Periacetabular osteotomy (PAO) is an elective reorientation surgery for the hip joint, typically for the treatment of hip dysplasia in young, otherwise healthy patients, which requires multiple pelvic osteotomies around the acetabulum [1]; a major source of its perioperative morbidity is blood loss [2]. The principal cause of postoperative blood loss after PAO is surgical trauma, with secondary activation of both the coagulation cascade and local fibrinolysis [3]. Tranexamic acid (TXA) is a synthetic derivative of the amino acid lysine that acts as competitive inhibitor of plasminogen activation, interfering with fibrinolysis [4]. Multiple studies and meta-analyses have shown that intravenous (IV) of TXA reduces postoperative bleeding and the need for transfusion after orthopedic surgery, including total joint arthroplasty, with no demonstrable change in the risk for postoperative complications, including venous thromboembolic events (VTE) [5-10]. However, there is no prospective data regarding TXA use for PAO, and, in our experience, PAO surgeons question and argue the use and disuse of TXA for this procedure.

In the PAO literature, allogeneic transfusion rates are as high as 58% [11], and blood loss can range to nearly 4 L [2, 11-17]. If autologous blood and intraoperative cell saver are considered along with allogeneic transfusions, the risk of perioperative transfusion can be as high as 94% [2].

Retrospectively, we reviewed 93 PAO cases performed by the principle investigator of this study. The average calculated blood loss was  $1.30 \pm 0.38$  L (range, 0.32 L – 2.65 L), and 33.3% of patients required at least one transfusion of allogeneic blood postoperatively. There has been one retrospective study examining the effect of IV TXA on blood loss and transfusion after PAO that showed that IV TXA may reduce total blood loss by 30.8% ( $p=0.001$ ) and transfusion rate by 58.6% ( $p=0.013$ )[11].

The goal of this randomized controlled, double-blinded trial is to assess the efficacy of IV TXA in reducing calculated total blood loss in patients undergoing PAO. Our specific objectives included analysis of (1) calculated total blood loss (primary outcome), (2) intraoperative cell saver utilization (secondary outcome), and (3) postoperative allogeneic blood transfusion (secondary outcome).

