**D. SAMPLE SIZE AND DATA ANALYSIS**

If you are uncertain about how to calculate your sample size and determine appropriate data analysis, please contact the Epidemiology and Biostatistics Core at [[contact]](mailto:[contact]) for assistance in completing this section.

*If this is a case series based only on the patients available and only descriptive statistics will be obtained, state this in lieu of a sample size calculation. However, if you propose a case series, but plan hypothesis testing (e.g., the calculation of p-values using statistical tests) you need to estimate your*

**Sample Size – Support estimates with evidence from the literature or prior studies and perform an appropriate sample size calculation.**

Proposed analysis (e.g., student's t-test, ANOVA, chi-square, regression, etc.):

Outcome variables of interest are all continuous. Two-sample t-test and multivariate linear regression will be utilized if the data is normally distributed; otherwise Mann-Whitney U test (non-parametric equivalent to the two-sample t-test) will be utilized.

1. Alpha level: 0.05
2. Beta or power level: 0.82
3. Primary outcome variable estimate (mean +/- s.d. for continuous outcome, frequency/percentage for categorical variable):

The primary outcome will be the calculated total blood loss, summarized as mean +/- s.d. Based on historical data of patients that underwent PAO or PAO/Scope without IV TXA, the mean calculated blood loss was approximately 1296 mL with a standard deviation of 383.27 mL.

4. Number of groups being compared (use 1 for paired analysis within the same subjects):

Two groups will be compared: treatment arm (up to 1 g of IV TXA diluted in 50 mL of normal saline) versus those receiving placebo (50 mL of normal saline)

5. Effect size or change expected between groups: 250 mL difference in blood loss
6. Resulting number per group: 40 per group
7. Total sample size required: 80

**Data Analysis - describe how the primary outcome will be analyzed and what types of statistical calculations will be used. Do the same for each secondary outcome. Reiterate briefly the main analysis to be done, which groups, which variables, possible confounders. Address how possible confounders will be identified and handled in the analysis.**

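### The printed equation for the primary endpoint does not return blood loss: red-cell volume is never converted to whole blood, and the transfusion term is divided by the hematocrit fall

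*Combined protocol and SAP*

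**What the plan says.** Section C.3(g) names the endpoint ("Primary outcome: Calculated total blood loss") and builds it in three steps, which Section D, Data Analysis, repeats.

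1. Estimated blood volume (EBV) comes from height, weight and sex.
2. "Multiplying the EBV by the hematocrit (Hct) gives the red blood cell (RBC) volume", so red-cell loss is EBV times the fall in hematocrit.
3. "Transfusions (mean volume per unit, mL) can be taken into account by calculating the total blood loss". Total loss in litres is the red-cell loss plus a term ending "No. of Units Transfused} \times 0.285) / (\text{Hct Preop} - \text{Hct Postop}) / 2".

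In short notation, with H for hematocrit: total = EBV × (Hpre − Hpost) + (units × 0.285) / (Hpre − Hpost) / 2.

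The postoperative value is described in two ways. Sections C.3(g) and D use "the lowest postoperative hemoglobin during the hospital stay (or the lowest postoperative hemoglobin prior to transfusion"). Section A.4 gives no equation, but its list of ingredients uses the last value before discharge: "final inpatient hemoglobin), and transfused hemoglobin".

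For planning, Section D states that "the mean calculated blood loss was approximately 1296 mL with a standard deviation of 383.27 mL". Section A.1 gives a range of 0.32 to 2.65 L for the 93 historical cases and says that "33.3% of patients required at least one transfusion of allogeneic blood postoperatively".

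**The concern.** A hematocrit-balance method has to divide the red-cell volume lost by a hematocrit to get back to whole blood. The printed equation has no such step. Its only divisor is the hematocrit difference, and that acts on the transfusion term alone. The two parts of the sum are therefore on different scales, and the second moves the wrong way: at a given number of units, a larger fall adds less.

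This is the sole primary outcome. The 250 mL target, the t-test, the adjusted regression and the interim boundary at p < 0.001 all depend on it. An analyst who follows the plan literally would test a quantity that cannot be read against 250 mL.

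**Working it through.** **Plan's own figure.** A two-sided t-test at 0.05 with 40 per arm, difference 250 mL and SD 383.27 mL has power 82.1% (noncentral t). The stated 82% reproduces, for a whole-blood quantity with that SD.

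**Example patient (assumed).** Woman, 1.65 m, 62 kg, preoperative hematocrit 0.39. With the printed coefficients, EBV = 0.3561 × 1.65³ + 0.03308 × 62 + 0.1833 = 3.834 L.

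**1. No transfusion, lowest hematocrit 0.29.**
- Printed: 3.834 × 0.10 = 0.383 L.
- Divided by mean hematocrit: 0.383 / 0.34 = 1.13 L.
- Divided by preoperative hematocrit: 0.383 / 0.39 = 0.98 L.

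The printed score is about a third of whole-blood loss on either divisor.

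**2. One unit transfused.**
- Lowest hematocrit 0.30: 3.834 × 0.09 + 0.285 / 0.09 / 2 = 1.93 L.
- Lowest hematocrit 0.24: 3.834 × 0.15 + 0.285 / 0.15 / 2 = 1.53 L.

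The score keeps falling until the drop reaches √(0.1425 / 3.834) = 0.193, or 19 points.

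**3. Other bracketings, minus sign kept, no transfusion.** If the whole sum is divided by the difference and then by 2, the hematocrit fall cancels and the score is EBV / 2 = 1.92 L. If it is divided by half the difference, the score is 2 × EBV = 7.67 L. Either result is the same however much the patient bled.

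**4. What happens to 250 mL.** Take true losses of 1.296 and 1.046 L in this woman, untransfused, under mean-hematocrit balance. The fall is 0.39 × loss / (EBV + loss / 2), which is 0.1128 and 0.0936. The printed scores are 3.834 × 0.1128 = 0.432 L and 3.834 × 0.0936 = 0.359 L. The 250 mL difference appears as about 73 mL.

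**5. Could the planning data have come from this equation?** Let p be the proportion transfused and d the difference in mean score between transfused and untransfused patients. The between-group variance p(1 − p)d² cannot exceed 0.383². With p = 1/3, d ≤ 0.813 L, so the untransfused mean is at least 1.296 − 0.813 / 3 = 1.025 L (0.98 L if 40% were transfused).
- Printed equation: this needs a mean fall of 1.025 / 3.834 = 26.7 points in the example woman (39% to about 12%), or 19.5 points in a man of 1.78 m and 80 kg (EBV 5.25 L).
- Mean-hematocrit divisor: 9.2 points in the same woman.
- Conversely, an untransfused mean of 0.383 L would require a transfused mean of (1.296 − 0.667 × 0.383) / 0.333 = 3.12 L, above the reported maximum of 2.65 L, and an overall SD of at least 0.471 × (3.12 − 0.38) = 1.29 L.

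**6. Postoperative value.** With one unit and a final value 5 points below baseline, the transfusion term alone is 0.285 / 0.05 / 2 = 2.85 L. It is undefined at no change and negative above baseline.

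**7. Illustrative power of the printed score.** Twenty-seven simulated scenarios used 40 per arm, a true difference of 250 mL, true-loss SD 383 mL and the lowest-value definition. Sex mix (10–30% male), baseline hematocrit and transfusion probability were assumed. Power was 26–41% for the t-test and 50–72% for Mann-Whitney, against 80–84% for true loss in the same runs.

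**The case against.** The strongest reply is that this is a transcription slip. The / 2 points to a mean-hematocrit divisor, the historical data look as if a working formula exists, and cited references stand behind the method. The text was also read from PDF by a program, so brackets or a sign could have been lost. All of that is plausible, and the sign and grouping should be checked against the original page. But the minus sign is the same in both places, no bracketing that keeps it works, and no other equation is given.

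Other points stand in part:

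- The reversal in step 2 holds at equal unit counts. Heavier bleeding may bring more units: two units at a lowest hematocrit of 24% score 3.834 × 0.15 + 0.570 / 0.15 / 2 = 2.48 L.
- The simulated power rests on assumed patients and on the printed equation actually being used. The plan's fallback for non-normal data is Mann-Whitney, so the t-test figures are the less favourable ones. If the historical values came from the corrected formula, the sample size is unaffected.
- Final versus lowest value is a contradiction in its own right and would survive a correct equation. It belongs here because it supplies the equation's input. The extreme and negative scores arise under the final-value reading, and nothing in the documents shows how often that would happen.
- Reinfused cell-saver blood has no term in the equation. That is a separate question, whether the endpoint is net or gross loss, and the repair below does not settle it.

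**Conclusion.** The concern holds and must be fixed before the endpoint is computed. As printed, the equation understates untransfused loss about threefold in the example patient and can rank transfused patients in the wrong order. A true 250 mL difference shrinks to about 73 mL in that untransfused patient.

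The algebraic fault needs no assumption about patients; the sizes do, since body size and hematocrits were chosen for illustration. That the historical 1296 ± 383 mL came from another formula is a strong inference from the plan's mean, SD, range and transfusion rate, not something the documents state. The 82% power is correct for whole-blood loss with that SD and does not carry over to the printed quantity.

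**What to change.** - **Equation.** In Sections C.3(g) and D print: total blood loss (L) = [EBV × (Hct Preop − Hct Postop) + units × 0.285] / [(Hct Preop + Hct Postop) / 2]. The mean-hematocrit divisor is inferred, so the sponsor should confirm it against the historical spreadsheet.
- **The 0.285 constant.** State whether it is red-cell volume or whole-unit volume. If it is whole-unit volume, at an assumed unit hematocrit of 0.55–0.65, one unit changes the result by 0.29–0.37 L at a lowest hematocrit of 30%.
- **Postoperative value.** Use one definition in Sections A.4, C.3(g) and D, and count only units given before that measurement. Adding a later unit to a pre-transfusion low of 24% turns 1.83 L into 2.73 L. Conversely, a pre-transfusion low ignores any bleeding after it, which the sponsor should weigh when choosing.
- **Planning data.** Before the interim analysis, confirm that 1296 ± 383 mL was computed with this equation. If not, restate the SD and power.

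The cost is one equation corrected in two places, one agreed definition and a check of the existing 93-case file. No new patients or data are needed.
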